5.2 Exclusion Criteria

A subject meeting any of the following exclusion criteria is NOT eligible for participation in the study.

1v5. Subjects with ACLF at Screening.

87 Ъ 24-Sep-2020 30 Effective Date Page Effective
 Number
 GLB-PRT-ALB-IG1601
 Version
 6.0
 Status
 Errect

 IG1601 - Prevention of Mortality with Long-Term Administration of Human Albumin in Subjects with
 6.0
 Status
 errect
Version 6.0 Decompensated Cirrhosis and Ascites GRIFOLS **Bioscience Industrial Group**

- 2v5. Subjects with type 1 HRS currently on treatment with vasoconstrictors or hemodialysis.
- 3. Subjects with TIPS or other surgical porto-caval shunts.
- 4v5. Subject with refractory ascites as defined by ICA criteria without any other event of acute decompensation (Appendix 2).
- 5v5. This criterion has been removed from protocol Version 5.
- 6v5. Subjects receiving dual anti-platelet therapy or anti-coagulant therapy (exception: DVT prophylaxis).
- 7v5. Subjects with ongoing endoscopic eradication of esophageal varices with ≤ 2 endoscopic sessions completed before screening.
- 8v5. This criterion has been removed from protocol Version 5.
- Subjects with evidence of current locally advanced or metastatic malignancy. Subjects with hepatocellular carcinoma within the Milan criteria [1 nodule ≤5 cm or 3 nodules ≤3 cm] [Appendix 6], non-melanocytic skin cancer, or controlled breast or prostate cancer can be included.
- 10v4. Subjects with acute or chronic heart failure (New York Heart Association [NYHA] Appendix 7).
- 11. Subjects with severe (grade III or IV) pulmonary disease (Global Obstructive Lung Disease [GOLD] Appendix 8).
- 12v5. Subjects with nephropathy with renal failure with a serum creatinine $\geq 2 \text{ mg/dL}$ or systemic hypertension.
- 13v5. This criterion has been removed from protocol Version 5.
- 14. Subjects with severe psychiatric disorders.
- 15. Subjects with a known infection with human immunodeficiency virus (HIV) or have clinical signs and symptoms consistent with current HIV infection.
- 16. Females who are pregnant, breastfeeding, or, if of childbearing potential, unwilling to practice effective methods of contraception (oral, injectable, or implanted hormonal methods of contraception, placement of an intrauterine device (IUD) or intrauterine system, condom, or occlusive cap with spermicidal foam/gel/cream/suppository, male sterilization, or true abstinence*) throughout the study.

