6.2 Sample Size

Based on the CANONIC study, the overall 1-year transplant-free mortality rate in the current study population is assumed to be about 46% (11,16). Assuming a potential drop-out rate of 20% and 5% type-1 error for a 2-sided Chi-square test, a global sample size of 410 patients (205 per treatment group) will allow an 80% statistical power to detect an absolute reduction of 15% (17) for the 1-year mortality rate in subjects treated with SMT + Albutein 20%.

GRIFOLS	Number	IG1601	Version	2.0	Status	Effective	Effective Date	09-Sep-2024	Page	22 of 52
BIG-CL-SP-000319 IG1601 Statistical Analysis Plan										

GRIFOLS	Number	BIG-CL-SP-000319		Version	2.0	Status	Effective	Effective Date	09-Sep-2024	Page	23 of 52
	IG1601 Statistical Analysis Plan										

Alternatively, the sample size was calculated based on the log-rank test as follows. Assuming the 1-year transplant or mortality rate is 46% for the control group, or equivalently, the transplant-free survival rate is 54%, which translates to a hazard rate of 0.0017 assuming an exponential distribution. Using a log-rank test at the 2-sided significant level of 5%, a total of 125 events would provide at least 80% power to detect an absolute reduction of 15% in transplant or mortality rate (a 31% 1-year transplant or mortality rate, or equivalently, a 69% transplant-free survival rate) in subjects treated with SMT + Albutein 20%. This absolute difference in transplant or mortality rates translates to a hazard ratio of 0.6022, or an approximate 40% risk reduction. With all subjects followed for the entire 1-year duration of the study, a total of 322 subjects would be required to obtain 125 events. Assuming a dropout rate of 20%, a global sample size of 404 subjects (202 per treatment group) is required. This sample size calculation was performed using Proc Power with the two-sample survival statement in SAS version 9.4.

Taking a conservative approach, the larger of the 2 sample sizes (i.e., 410 subjects based on the Chi-square test) will be used to ensure the study has sufficient power.

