6.5 Hypothesis Testing and Multiplicity Adjustments

All statistical tests will be 2-sided with significance level fixed at 0.05.

The fixed-sequence testing method will be used to adjust for multiplicity in the analyses of the secondary efficacy endpoints (using the ITT population). Specifically, the superiority of SMT + Albutein 20% versus SMT alone for the secondary efficacy endpoints will only be tested if the superiority for the primary efficacy endpoint is demonstrated at the 2-sided significance level of 5% (for ITT population).

For the secondary efficacy endpoints, each subsequent hypothesis is tested only if the superiority for the previous comparison(s) listed below has been demonstrated at a 2-sided significance level of 5%. The order in which the null hypotheses will be tested is predetermined for the secondary efficacy endpoints as follows:

1. Time to death through 1 year after randomization
2. Time to liver transplantation or death through 6 months after randomization
3. Time to death through 6 months after randomization
4. Time to liver transplantation or death through 3 months after randomization
5. Time to death through 3 months after randomization
6. Total number of paracenteses
7. Incidence of refractory ascites according to the ICA criteria

No other adjustments for multiplicity are planned. P-values will be displayed for all the above pre-specified tests for completeness; interpretation and reporting of significant hypothesis test results will follow the fixed sequence approach described.

GRIFOLS	Bioscience Industrial Group	Number	IG1601	Version	2.0	Status	Effective	Effective Date	09-Sep-2024	Page	24 of 52
		IG1601	Statistical Analysis Plan								

7 Subject Disposition and Demographics

Unless otherwise noted, all demographics listings and summaries will be based on the ITT population. Subjects who were incorrectly stratified at the time of randomization will be listed and summarized.

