7.3 Demographics

Demographics (age, sex, race, ethnicity, country and region in Europe), baseline weight, and stratification factors for randomization will be listed and summarized. Subjects who were incorrectly stratified at the time of randomization will be listed and summarized.

Baseline characteristics listed above will be compared to evaluate possible imbalance by using Student's t test will be used for continuous variables, Chi-square test for binomial or nominal variables, and Poisson model for count variables (with adjustment for overdispersion). All demographic and baseline characteristics data will be listed. Summaries will be provided by treatment group for ITT.

In addition, the following baseline characteristics will be summarized; ACLF Grade, Ascites Grade, Ascites Refractory Occurrences, Ascites Refractory Type, CLIF-C ACLF Score, CLIF-C AD Score, CLIF-C OF Total Score, Child-Pugh Score, MELD Score.

GRIFOLS	IG1601 Statistical Analysis Plan			
	Number	BIG-CL-SP-000319	Version	2.0
	Status	Effective	Effective Date	09-Sep-2024
	Page			25 of 52

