9.2.6 Total Number of Paracenteses

For each subject, the total number of reported paracentesis procedures on treatment will be calculated and summarised by treatment group.

A paracentesis procedure occurring on treatment will be defined as any paracentesis procedure that occurred with a start date/time on or after the subject's date/time of randomization (for SMT alone group) or commencement of Albutein (for SMT+ Albutein treatment group). If time is missing and the procedure occurred on or after the date of randomization (for SMT alone group) or the date of commencement of Albutein

(for SMT+ Albutein treatment group) it will be considered to have occurred while on treatment.

The rate of occurrence of paracenteses will be analyzed using Poisson regression with adjustment for overdispersion using the Pearson statistic to estimate the scale parameter.

- Null hypothesis H_0 : The rate of occurrence of paracentesis procedures SMT + Albutein 20% is greater than or equal to the rate of occurrence of paracentesis procedures on SMT alone. [i.e. $Rate\ ratio\ (SMT+Albutein\ 20\% \ vs \ SMT\ Alone) \geq 1$].
- Alternative hypothesis H_a : The rate of occurrence of paracentesis procedures on SMT + Albutein 20% is less than the rate of occurrence of paracentesis procedures on SMT alone. [i.e. $Rate\ ratio\ (SMT+Albutein\ 20\% \ vs \ SMT\ Alone) < 1$].

The rate of occurrence of paracentesis procedures in the SMT + Albutein 20% treatment group will be compared to the rate of occurrence of paracentesis procedures in the SMT alone group. The response variable in the model will be the total number of procedures experienced by a subject while on treatment. The model will include treatment group, IWRS stratification factors of region (Europe or North America) and history of hospitalization for acute decompensation of liver cirrhosis (yes or no) as factors. The logarithm of the subjects' treatment duration will be used as an offset variable in the model to adjust for subjects having different exposure times during which the events could occur. The estimated treatment effect (i.e. the incidence rate ratio of SMT + Albutein 20% versus SMT alone) and corresponding 95% confidence interval (CI) will be presented.

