9.2.7 Incidence of Refractory Ascites

The number and percentage of subjects with at least one incidence of refractory ascites on treatment will be presented by treatment. Incidence of refractory ascites occurring on treatment is defined as any incidence that occurred with a start date/time on or after the subjects date/time of randomization (for SMT alone group) or commencement of Albutein (SMT+ Albutein treatment group) treatment. If time is missing and the incidence occurred on or after the date of randomization (for SMT alone group) or the date of commencement of Albutein (for SMT+ Albutein treatment group) treatment it will be considered to have occurred while on treatment.

A chi-square test will be used to assess if there is an association between treatment and incidence of refractory ascites.

Null hypothesis H_0 : $P1 = P2$

Alternative hypothesis H_a : $P1 \neq P2$

GRIFOLS	Number	IG1601	IG1601 Statistical Analysis Plan
	Version	2.0	
	Effective		
	Effective Date	09-Sep-2024	
	Page	33	of 52

where P1 is the proportion of subjects with at least one incidence of refractory ascites in the SMT + Albutein 20% treatment group and P2 is the proportion of subjects with at least one incidence of refractory ascites in the SMT alone treatment group. A two-sided chi-square test at a significance level of significance of 0.05 will be performed.

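### The refractory-ascites endpoint (SAP 9.2.7) tests incidence in all ITT subjects although some may have the condition at entry; its only safeguard is a start-date rule that leaves ongoing and Day 1 records unsettled

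*SAP*

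**What the plan says.** **Eligibility.** Protocol 5.2, criterion 4v5, excludes a "Subject with refractory ascites as defined by ICA criteria without any other event of acute decompensation". Refractory ascites accompanied by another decompensation event is therefore not a bar to entry.

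**Baseline data.** SAP 7.3 lists "ACLF Grade, Ascites Grade, Ascites Refractory Occurrences, Ascites Refractory Type" among the baseline characteristics to be summarized, so the status is captured and subjects with it are expected.

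**Secondary test 7.** SAP 9.2.7 states: "The number and percentage of subjects with at least one incidence of refractory ascites on treatment will be presented by treatment". The groups are compared by a two-sided chi-square without covariates, in the ITT population (SAP 9.2). An incidence counts if it starts at or after randomization (control) or the first infusion (albumin arm). If the time is missing and the date is that day or later, it also counts.

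**Secondary test 6.** For paracenteses, SAP 9.2.6 states: "The model will include treatment group, IWRS stratification factors of region (Europe or North America) and history of hospitalization", with log treatment duration as offset and a Pearson-estimated scale. There is no ascites term.

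**Elsewhere.** The exploratory TIPS model (SAP 9.3.10) does include baseline occurrence. The baseline-imbalance analysis in SAP 9.1.3 is a Cox model for the primary endpoint only. The per-protocol repeat of the secondary analyses does not deal with baseline ascites status.

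**The concern.** A subject who enters with refractory ascites cannot develop it anew, yet stays in the denominator of an incidence endpoint. What happens in the numerator is not fully settled. ICA ascites assessments recur at Day 1, Day 11, monthly and Month 12, and the SAP does not say whether an ongoing case recorded at one of these counts. If it does, the endpoint mixes existing with new disease and the contrast moves toward no effect.

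The SAP is also inconsistent about Day 1. Under SAP 6.1.3 an untimed assessment on the randomization date is taken as baseline. Under SAP 9.2.7 an untimed incidence on that date is taken as on treatment. Protocol 7.2.1.2.1 places the Day 1 ascites assessment before treatment, so one untimed record could be both a baseline characteristic and an event.

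For paracenteses, subjects with refractory ascites plausibly need the most procedures. Leaving their status out of the model adds between-subject variance.

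**Working it through.** **1. The plan's own figure.** Inputs from SAP 6.5 and 6.2: "All statistical tests will be 2-sided with significance level fixed at 0.05"; "the overall 1-year transplant-free mortality rate in the current study population is assumed to be about 46" per cent; "will allow an 80% statistical power to detect an absolute reduction of 15" points; "Assuming a potential drop-out rate of 20% and 5% type-1 error for a 2-sided Chi-square test". With p1 = 0.46, p2 = 0.31 and mean 0.385:

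n per arm = [1.96·√(2·0.385·0.615) + 0.842·√(0.46·0.54 + 0.31·0.69)]² / 0.15² = (1.349 + 0.572)² / 0.0225 ≈ 164

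164/0.8 = 205 per arm, 410 in total, with 80.0% power at 164 evaluable per arm. (Rounding up to 165 first gives 207 per arm, 414 in total.) The figure reproduces. It concerns the primary endpoint; neither ascites endpoint has a stated power or expected rate.

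**2. Effect on secondary test 7.** Let q be the share with refractory ascites at entry, and let c and t be the new-onset risks in control and albumin subjects free of it. The documents give none of these. Assumed: q = 10–30%, c = 30%, t = 18% (risk ratio 0.60), 205 per arm.

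- A, prevalent cases never counted but kept in the denominator: risks (1−q)c and (1−q)t.
- B, prevalent cases re-recorded and counted: risks q+(1−q)c and q+(1−q)t.
- C, only subjects at risk: risks c and t, with 205(1−q) per arm.

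In A and B the difference is (1−q)(c−t). In A the risk ratio stays at 0.60; in B it moves toward 1. Example for B at q = 20%: 0.20 + 0.80·0.30 = 0.440 against 0.20 + 0.80·0.18 = 0.344, a ratio of 0.78.

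Power is that of the same two-sided 5% two-proportion test. With q = 0 it is 81%.

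| q | Difference, A and B (points) | Power A | Risk ratio B | Power B | Power C (n per arm) |
|---|---|---|---|---|---|
| 10% | 10.8 | 75.9% | 0.71 | 65.3% | 77.1% (184) |
| 20% | 9.6 | 69.5% | 0.78 | 51.2% | 72.2% (164) |
| 30% | 8.4 | 62.4% | 0.84 | 39.9% | 66.6% (144) |

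Loss against C is 1.2, 2.7 and 4.2 points under A, and 11.8, 21.0 and 26.7 points under B. Assumed risks of 25% against 15%, or 40% against 27%, show the same pattern.

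**3. Effect on secondary test 6.** Simulation with 700 runs per setting, 410 subjects, 3 procedures a year, true rate ratio 0.70, gamma heterogeneity with shape 1, variable follow-up, refractory subjects at 4 times the rate, q = 10/20/30% (all assumed):

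- Estimated rate ratio: 0.70–0.71 with or without the baseline term.
- SD of the log rate ratio: 0.166/0.166/0.153 without the term, 0.149/0.147/0.140 with it. The squared ratios are 1.24/1.28/1.19.
- Power with robust standard errors: 59/59/63% without the term, 69/68/72% with it. At twice the rate the gain is only 2–5 points.
- Type I error with the term: 11.6/13.4/12.4% with Pearson scaling, 6.6/6.1/6.0% with robust standard errors. The Monte Carlo standard error at 5% is √(0.05·0.95/700) = 0.8 points, so the Pearson excess is not chance.

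A second simulation set gave SDs of 0.13–0.16 with the term and 0.14–0.18 without it, and type I error of 10–17% (Pearson) against 4–7% (robust). Over an assumed 3–5 fold rate the efficiency gain is about 1.1–1.5 times.

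**The case against.** The start-date rule is real baseline handling. Read literally, a case that began before Day 1 is never an event. That is row A: the risk ratio is intact and the loss is 1–4 points. This stands, and a reader who inferred that the SAP ignores baseline status altogether would be wrong. The rule does not, however, take these subjects out of the denominator or settle ongoing and untimed Day 1 records.

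A reader might also infer that prevalent cases will be counted, so that the risk ratio will be as weak as 0.84 and power as low as 40%, or that open-label sites will re-date ongoing disease. The documents do not support either inference. The eCRF completion rules are not in them, and row B is what an unsettled rule permits, not what the plan prescribes.

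For paracenteses, adjusting for the randomization factors alone is a defensible choice. Randomization keeps the rate ratio unbiased, so reading the omission as bias is unsupported. Nor should the gain be judged from the adjusted model's Pearson-scaled standard error of about 0.11, which would suggest 1.3–2.3 times the sample. That standard error is too small, as the inflated type I error shows.

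Finally, these are tests 6 and 7, formally reached only after the primary endpoint and all five survival secondaries succeed. That limits the consequence. The p-values will nonetheless be displayed for every test in the sequence (SAP 6.5), and both endpoints belong to a stated secondary objective.

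**Conclusion.** The point holds for SAP 9.2.7: the population, endpoint and counting rules do not fit an incidence question when prevalent cases may be enrolled. The dilution of the absolute difference by the factor (1−q) follows from the design whichever counting rule applies. The power cost depends on that rule: about 1–4 points if prevalent cases never count, about 12–27 if re-recorded cases do, for q of 10–30% and assumed risks of 30% against 18%. The true prevalence and risks are not in the documents, so these figures show a range and do not forecast the result.

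For SAP 9.2.6 the issue is precision only, and the gain depends on how much more often refractory subjects undergo paracentesis. Both changes are worth making. Neither touches the primary analysis or the sample size of 410.

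**What to change.** **SAP 9.2.7.** Make the formal test one of first new onset in randomized subjects free of refractory ascites at the Screening/Day 1 ICA assessment, analysed by randomized group. Alternatively, keep all ITT subjects and stratify the test by baseline refractory status; if every prevalent case is handled alike, that stratum adds nothing to the contrast, so the information is essentially the same. In either case, state that persistent cases and pre-treatment Day 1 records are baseline findings and not events, and reconcile the missing-time rule with SAP 6.1.3. Report the all-ITT proportion as supportive.

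Cost: with restriction, somewhat fewer subjects in the test (184, 164 or 144 per arm at 10, 20 or 30% prevalence), none of whom is lost as a source of information on new onset. Protocol 9.7 and SAP 6.4.2 specify ITT for all efficacy analyses, so restriction is a departure to be recorded in SAP section 12. Stratifying avoids the change of population but is still a change of test to record there.

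**SAP 9.2.6.** Add baseline refractory status (yes/no) and baseline ascites grade to the Poisson model, and replace the Pearson-scaled standard error with a robust (sandwich) one. The covariates should not be added while the Pearson scale is kept. The data are already collected, so the cost is SAP text and programming.

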5.3.5 Follow-up of Subjects Withdrawn from Study

If possible, blood samples will be obtained to complete all pertinent tests at the time of subject withdrawal. In all cases, the reason for withdrawal must be recorded in the eCRF and in the subject's records. No subject can be re-enrolled into the study after having been withdrawn from the study.

Subjects who receive any amount of IP and discontinue early from the study should have all Month 12/Early Discontinuation visit procedures performed at the time of withdrawal (preferably within 1 week of withdrawal).

All efforts should be made to collect the vital status of the subject (including data on liver transplantation, subject survival, and cause of death) at Months 3, 6, and 12.

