7.2.1.4 Follow-Up for Early Discontinued Subjects (Months 3, 6, 12)

In subjects who discontinue from the study early, the following assessments will be performed at Months 3, 6, and 12:

• Record data on liver transplantation, subject survival, and cause of death

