5.2.7 Follow-Up for Early Discontinued Subjects (Months 3, 6, and 12)

In subjects who discontinue from the study early, data on liver transplantation, subject survival, and cause of death will be obtained at Months 3, 6, and 12.

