9.2.7.1 Secondary Efficacy Sensitivity Analyses

The secondary analysis described for each of the secondary endpoints listed above will be repeated using the per-protocol population as a sensitivity analysis.

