9.3.1 Incidence of ACLF at 3, 6 and 12 Months

ACLF is evaluated monthly through Month 12 and will be listed.

The number and percentage of subjects with at least one occurrence of ACLF from Month 1 through Month 3 will be presented by treatment, and treatment differences will be analyzed by the Chi-square test. Month 1 is inclusive of the occurrences reported at the Day 11 and Month 1 scheduled visits.

The same summary and analysis will be performed for the ACLF evaluations occurring from Month 1 through Month 3, from Month 1 through Month 6, and for all ACLF evaluations occurring from Month 1 through Month 12.

GRIFOLS	Number	BIG-CL-SP-000319	Version	2.0	Status	Effective	Effective Date	09-Sep-2024	Page	34 of 52
	IG1601	Statistical Analysis Plan								

In addition, the ACLF evaluations will be summarized by treatment group for each visit, reporting number and percentage of subjects reporting ACLF and the ACLF grade by visit.

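### SAP 9.2.7 counts early study leavers as free of refractory ascites in an unstratified chi-square, so the comparison depends on dropout by arm; a stratified test and a supplementary time-to-event analysis would be a cheap improvement

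*SAP*

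**What the plan says.** SAP 9.2.7 tests P1 = P2 at a two-sided 5% level, "where P1 is the proportion of subjects with at least one incidence of refractory ascites in the SMT + Albutein 20% treatment group" and P2 is its SMT counterpart. The test is "A chi-square test will be used to assess if there is an association between treatment and incidence of refractory ascites". It has no stratification, no time at risk and no rule for subjects who die or leave the study. The on-treatment definition has a start but no end.

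After early study discontinuation, SAP 5.2.7 says "data on liver transplantation, subject survival, and cause of death will be obtained at Months 3, 6, and 12". Protocol 7.2.1.4 agrees: "In subjects who discontinue from the study early, the following assessments will be performed at Months 3, 6, and 12", and its list contains only transplant, survival and cause of death. Protocol 5.3.5 likewise aims at survival information: "All efforts should be made to collect the vital status of the subject". Ascites is not followed after a subject leaves.

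The only sensitivity analysis for this endpoint is in SAP 9.2.7.1: "The secondary analysis described for each of the secondary endpoints listed above will be repeated using the per-protocol population as a sensitivity analysis".

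Other endpoints vary. For paracenteses (SAP 9.2.6), log treatment duration "will be used as an offset variable in the model to adjust for subjects having different exposure times". For ACLF incidence (SAP 9.3.1), "treatment differences will be analyzed by the Chi-square test", with no time at risk, as here.

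In the fixed sequence of SAP 6.5, refractory ascites is seventh of seven secondaries.

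**The concern.** Two separate matters arise.

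The first is missing follow-up. A subject who leaves the study at month 2 cannot be seen to develop refractory ascites at month 5, yet stays in the ITT denominator as event-free. Each arm's proportion is then too low by an amount that depends on that arm's dropout. The trial is open-label and one arm attends for an infusion every 10 days, so equal dropout cannot be taken for granted. SAP 6.2 gives one dropout figure, 20%, not split by arm.

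The second is a matter of target. If Albutein prolongs transplant-free survival, its subjects spend longer at risk of ascites. The proportion then shows a smaller benefit than the hazard while at risk. A reader who sees only the proportion may misjudge the effect on ascites itself.

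At stake is the reading of one secondary result, plus a little precision lost by ignoring the stratification factors.

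**Working it through.** **Inputs from the documents (SAP 6.2):** one-year death or transplant 46% on SMT and 31% on Albutein; dropout 20%; 205 per arm.

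**Assumed, because the documents give no refractory-ascites rate:** SMT ascites hazard r = 0.25, 0.5 or 1.0 per year; cause-specific HR 0.70, with 0.60 and 0.50 as checks; constant and independent hazards; everyone event-free at entry; ascites follow-up ending at death or transplant.

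**1. The plan's own figures.** HR = ln(0.69)/ln(0.54) = 0.6022, as stated. The two-proportion formula for 46% vs 31% at 80% power gives 164.0 per arm; 164/0.8 = 205, or 410 in total, as stated.

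**2. Time at risk.** The death/transplant hazards are -ln(0.54) = 0.616 (SMT) and -ln(0.69) = 0.371 (Albutein). With total competing hazard c, mean time at risk over one year is (1 - exp(-c))/c.
- No dropout: 0.747 vs 0.835 years, ratio 1.12.
- 20% dropout in both arms (add -ln(0.8) = 0.223): 0.677 vs 0.754 years, ratio 1.11.

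**3. Effect of unobserved follow-up.** The proportion with an event is I(r, c) = r/(r + c) × (1 - exp(-(r + c))). The true cumulative incidence uses c for death/transplant only; the crude proportion adds the dropout hazard. With r = 0.5 on SMT and 0.35 on Albutein (HR 0.70):
- True: I(0.5, 0.616) = 30.1%; I(0.35, 0.371) = 24.9%; difference 5.2 points.
- Crude SMT at 20% dropout: I(0.5, 0.839) = 27.6%.

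| Albutein dropout | Crude Albutein | Crude difference (true: 5.2) |
|---|---|---|
| 10% | 23.8% | 3.7 |
| 20% | 22.6% | 4.9 |
| 30% | 21.4% | 6.1 |
| 40% | 20.1% | 7.4 |

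Both arms' proportions are always too low. The difference is too small at 10 and 20% Albutein dropout and too large at 30 and 40%. The other assumed hazards show the same pattern: at r = 0.25 the true difference is 3.2 and the crude ones are 2.4, 3.0, 3.7 and 4.4; at r = 1.0 the true difference is 6.6 and the crude ones are 4.6, 6.5, 8.5 and 10.6.

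**4. Proportion against hazard.** Compare the difference under planned survival with the difference if Albutein had SMT's survival, without dropout, at HR 0.70:
- r = 0.25: 3.2 vs 4.6 points, 30% smaller.
- r = 0.5: 5.2 vs 7.7 points, 33% smaller (from unrounded values).
- r = 1.0: 6.6 vs 10.7 points, 38% smaller.

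The shortfall is 19-25% at HR 0.60 and 13-17% at HR 0.50. With 20% dropout in both arms these shares fall by 1 to 3 points. Equal total competing hazard, which removes the difference in time at risk, needs Albutein dropout of 1 - exp(-(0.616 - 0.371 + 0.223)) = 37%.

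**5. Missing strata.** If two equal-sized strata differ by 10 to 20 points around 30%, they explain 0.05²/0.21 to 0.10²/0.21 of the variance, about 1 to 5%.

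**The case against.** The strongest defence is that the SAP names its target and tests it validly. With complete follow-up, the proportion is the cumulative incidence in the presence of death and transplant, a sensible total-effect measure. No document makes the cause-specific hazard the target. That stands, and it defeats two readings a reader might infer.

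- *The chi-square has inflated type I error, or needlessly gives up power.* With ascites HR 1 and better survival, the proportions truly differ (30.1% vs 33.4% at r = 0.5 without dropout). Rejecting P1 = P2 there is a correct finding about proportions. Setting its power beside that of a log-rank test compares two different null hypotheses.
- *The test in the sequence should be replaced by a log-rank test.* Protocol 9.1.2.2 names Fisher's exact or chi-square for binomial endpoints. A cause-specific analysis answers a different question and is open to informative censoring. Swapping is a trade-off, not a correction.

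Two further points stand. Protocol 5.3.2 keeps transplanted subjects, and those who stop treatment for TIPS or listed severe events, on their planned visits, so it is study discontinuation, not treatment discontinuation, that loses ascites data. SAP 6.5 displays every p-value but ties interpretation to the fixed sequence.

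The defence does not answer the missing follow-up of study leavers. The proportion is a clean cumulative incidence only if they are handled, and the per-protocol repeat counts its own leavers in the same way.

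**Conclusion.** The point holds as a cheap improvement. Counting study leavers as event-free understates refractory-ascites incidence in both arms and makes the treatment difference depend on dropout by arm. In the worked case a true difference of 5.2 points appears as anything from 3.7 to 7.4 points.

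It is tempting to conclude that the distortion always works against Albutein. The documents do not support that: it requires similar dropout, and no dropout figures by arm are given. The smaller effect on the proportion than on the hazard (30-38% of the absolute difference at HR 0.70, under the planned survival) is a difference in target that should be stated, not an error.

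The consequence is limited: last place in the sequence, interpretation bound to that sequence, and no bearing on the primary. All sizes rest on assumed ascites hazards, constant independent hazards and an event-free start. The last is not assured, because Protocol 5.2 excludes refractory ascites only when no other decompensation event is present.

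**What to change.** Keep the proportion as the seventh secondary endpoint, but test it with a Cochran-Mantel-Haenszel test stratified by the two IWRS factors.

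Before database lock, and without looking at ascites data by arm, prespecify a supplementary ITT analysis of time from randomization to first refractory ascites:
- (a) cumulative incidence by arm with death and transplant as competing events. Censor study dropouts at their last ascites assessment, and everyone else at randomization + 361 days at the latest. Do not use the SAP 6.1.4 last-contact date, which includes contacts that give survival status only;
- (b) a cause-specific Cox hazard ratio stratified by the IWRS factors;
- (c) a repeat in subjects without refractory ascites at baseline (summarized under SAP 7.3), for whom first onset is well defined.

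State that the hazard ratio and the proportion answer different questions and are to be read together. Record the additions in SAP section 12.

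Cost: one revised subsection, a few extra outputs and one section 12 entry; event start dates, ascites assessments and strata are already collected. The main downside is that censoring may be informative if ascites, death and dropout share frailty, which could distort the cause-specific hazard ratio; this should be said when the result is reported.
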